6.1. General Principles

For the purposes of this SAP, all data processing, summarization and analyses will be performed using [REDACTED] Drug Development's SAS Environment / Version 9.4 (or later) of the SAS® statistical software package. When summarizing data by treatment group, results will be combined across the study periods. For example, the data from subjects who received SB-121 in Treatment Period 1 will be combined with the data from subjects who received SB-121 in Treatment Period 2. An additional analysis will be done for change of certain parameters to end of Treatment Period 1 and end of Treatment Period 2, respectively, utilizing as Baseline values the last observation prior to dosing in Treatment Period 1. This will be done for each treatment group. These parameters may include fecal calprotectin and lactoferrin, serum hs-CRP and tumor necrosis factor- α , and plasma oxytocin and vasopressin levels.

The default summary statistics for quantitative variables will be the number of observations (n), mean, standard deviation (SD), median, minimum (min) and maximum (max), for those subjects with data.

For qualitative variables, the number (n) and percentage (%) of subjects with non-missing data per category will be the default summary presentation, and where appropriate and present, the number of missing values as a “Missing” category. Number of subjects in the analysis population will be used as denominator for percentages calculation, unless stated otherwise in TFLs mock shell(s).

For the TFLs, the laboratory results will be summarized or presented in International System of Units (SI) units.

Specifications for table, figures and data listing formats can be found in the TFL shells specifications for this study. Please refer to “2. General Format Guidelines” section within TFL shells for more details on presentation of results.

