7.2. Rationale and Discussion of Study Design

SB-121 is being developed for use in the treatment of AD in patients age 36 months and above.

This study is a multiple-dose, randomized, double-blind, placebo-controlled, cross-over single-site Phase I study. The primary objective is to evaluate the safety and tolerability of multiple doses of SB-121 in subjects ages 15 to 45 years with AD.

Additionally, multiple behavioral and physiological measures of AD, as well as mechanistic biomarkers, will be assessed in order to inform later stage trials.

A placebo control is used in the present study to enable assessment of safety of SB-121.

The study is being conducted in a double-blind fashion to reduce the risk of bias in the reporting of study outcomes by subjects and investigators. A cross-over design will enable each patient to be a control for her/himself, thus increasing the power to detect target engagement in a first in disease study while also increasing available safety data by exposing all subjects to the IP.

[figure not shown]

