5.1.2. Screening / Baseline Period

For all subjects, the screening period will be defined as the period from informed consent to the first dose of treatment in Treatment Period 1.

Baseline values for analyses of Treatment Period 1 will be the last observation prior to dosing in Period 1. Baseline values for analyses of Treatment Period 2 will be the last observation after the Treatment Period 1 washout and prior to dosing in Treatment Period 2. An additional analysis will be done for change of certain parameters, as discussed in Section 6.1, to the end of Treatment Period 1 and to the end of Treatment Period 2, respectively, utilizing as Baseline values the last observation prior to dosing in Treatment Period 1. This will be done for each treatment group.

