6.6.2. Secondary Analysis

[REDACTED]. These measures are: Clinical Global Impressions Severity and Improvement Subscales, Vineland Adaptive Behavior Scales (3rd edition), Aberrant Behavior Checklist, Woodcock Johnson Test (3rd Edition), Repeatable Battery for Assessment of Neuropsychological Status (RBANS), Test of Attentional Performance for Children (KiTap), Neurophysiology Measures including EEG resting state, auditory habituation, and chirp modulated sweep auditory evoked response, and Eye Tracking and Pupillometry measures.

The number and percentage of subjects with incidence of presence of Sephadex® microspheres in the stool and incidence of symptomatic bacteremia with positive *L. reuteri* identification will be summarized by treatment group by visit and listed based on the ITT population.

The stool and blood samples will be used for the evaluations of potential biomarkers of inflammation (fecal calprotectin and lactoferrin and blood hs-CRP and tumor necrosis factor- α). In accordance with the baseline value definition in Section 5.1.2, the absolute change from baseline will be derived as follows:

Absolute change (unit) = (post-baseline value – baseline value)

The following will be summarized by treatment group for the ITT population:

- Observed values and percentage change from baseline at each assessed visit, including comparison of baseline to end of Treatment Period 1 and baseline to end of Treatment Period 2, for each biomarker parameter using summary statistics for continuous variables;

A listing of all biomarkers data including derived change from baseline will be provided for the Safety population.

Plasma oxytocin and vasopressin levels will also be analyzed. In accordance with the baseline value definition in Section 5.1.2, the absolute change from baseline will be derived as follows:

Absolute change (unit) = (post-baseline value – baseline value)

The following will be summarized by treatment group for the ITT population:

- Observed values and percentage change from baseline at each assessed visit, including comparison of baseline to end of Treatment Period 1 and baseline to end of Treatment Period 2, for each parameter using summary statistics for continuous variables;

A listing of all plasma oxytocin and vasopressin data including derived change from baseline will be provided for the ITT population.

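### For six blood and stool markers the SAP never summarises the within-subject SB-121 versus placebo difference; adding it is a cheap improvement, not the correction of an error

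*SAP*

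**What the plan says.** Protocol 7.2 gives two reasons for the crossover. The first is self-control: "A cross-over design will enable each patient to be a control for her/himself, thus increasing the power to detect target engagement". The second is exposure: "while also increasing available safety data by exposing all subjects to the IP".

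SAP 6.1 sets the general rule for tables: "When summarizing data by treatment group, results will be combined across the study periods". The default statistics are n, mean, SD, median, minimum and maximum. SAP 6.1 also states: "An additional analysis will be done for change of certain parameters to end of Treatment Period 1 and end of Treatment Period 2", measured from the Period 1 baseline and shown for each treatment group; it names the six markers as candidates. For the main change analysis, SAP 5.1.2 uses period-specific baselines: "Baseline values for analyses of Treatment Period 2 will be the last observation after the Treatment Period 1 washout".

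SAP 6.6.2 applies this to the six markers. The only difference it defines is post-baseline minus baseline ("the absolute change from baseline will be derived as follows"). The summaries it commits to are: "Observed values and percentage change from baseline at each assessed visit, including comparison of baseline to end of Treatment Period 1", and likewise to the end of Period 2. Subject listings are planned as well. Protocol 13.1.6 plans descriptive statistics for the inflammation biomarkers and sends the autism measures to a separate plan. Layouts are held elsewhere: "Specifications for table, figures and data listing formats can be found in the TFL shells specifications for this study".

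**The concern.** The second reason in Protocol 7.2 is served by the SAP: everyone is exposed and the safety data are pooled by treatment. The first is not visibly served for these six markers. Every planned summary describes one treatment, or one treatment in one period. None takes each subject's SB-121 value minus the same subject's placebo value and reports the mean, SD or precision of that difference.

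This matters most for oxytocin. Its circulating level is a secondary objective and Protocol 5.1 names oxytocin signalling as the hypothesised mediator. Protocol 7.2 also says that mechanistic biomarkers are measured to inform later trials. The SD of the within-subject difference is what a later crossover would need for its sample size, and it cannot be recovered from two marginal SDs without knowing the correlation between them.

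**Working it through.** **No figure to reproduce.** Protocol 13.2 and SAP 2.3 say that the sample size has no statistical basis. No effect size, SD, correlation or dropout rate is given.

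**Inputs.** From the documents: up to 16 subjects, 1:1, so 8 per sequence, all crossing over. Assumed: all 16 complete, SD = 1 for each marker value, and one correlation rho between any two values of the same subject, baselines included.

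**1. Paired difference in end-of-period values.** Its variance is 2(1 - rho), so SE = sqrt(2(1 - rho)/16). Averaging the two sequence means of 8 gives the same SE: 0.5 × sqrt(2 × 2(1 - rho)/8). The 95% half-width uses t on 14 df, 2.145.

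**2. What a reader could build from the planned tables.** The SAP plans no such interval.
- Observed-value columns treated as unpaired: SE = sqrt(2/16) = 0.354, half-width 0.722 on 30 df.
- By-period absolute-change cells of 8: SE = 0.5 × sqrt(4 × 2(1 - rho)/8). The ratio to the paired SE is sqrt(2) = 1.41 at every rho.

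| rho | Paired SE | Paired half-width | Observed columns: SE / half-width | By-period change cells: SE |
|---|---|---|---|---|
| 0 | 0.354 | 0.76 | 0.354 / 0.72 | 0.500 |
| 0.3 | 0.296 | 0.63 | 0.354 / 0.72 | 0.418 |
| 0.5 | 0.250 | 0.54 | 0.354 / 0.72 | 0.354 |
| 0.7 | 0.194 | 0.42 | 0.354 / 0.72 | 0.274 |

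**3. Break-even.** At rho 0 the paired half-width is 0.758 because it has fewer df. It equals 0.722 when sqrt(1 - rho) = 0.722/0.758 = 0.953, so rho is about 0.09. Below that the interval does not narrow. Protocol 5.1 describes oxytocin as secreted in pulses with a very short half-life, so a low rho between single draws is possible for that marker.

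**4. Does the point estimate change?**
- Observed values, full completion: no. The difference of the pooled means is the mean of the differences.
- By-period absolute change: no. The Period 1 baseline cancels within each subject, so the period-balanced contrast equals the period-adjusted paired difference.
- Percentage change: yes. Two percentage changes differ by 100 × (y1 - y2)/baseline, so the baseline does not cancel.
- Change from period-specific baseline: yes, because two different baselines are subtracted.

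**5. Pairing changes from period-specific baselines.** The covariance of a subject's two changes is rho - rho - rho + rho = 0, so SE = sqrt(4(1 - rho)/16) = 0.418/0.354/0.274 at rho 0.3/0.5/0.7. Pairing these gains no precision under this model; their use is as a carryover check.

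**6. Carryover.** Let tau be the treatment effect, and let an SB-121 shift L persist to the end of Period 2 in the SB-121-first sequence. That sequence then gives tau - L, the other gives tau, and the average is tau - L/2. If the full shift is already present at the Period 2 baseline and stays, it cancels in absolute change from that baseline.

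**7. Incomplete Period 2.** If 1, 2 or 3 of 8 in one sequence only miss Period 2, the Period 2 share differs between the pooled observed-value columns by 8/16 - 7/15 = 3.3%, 8/16 - 6/14 = 7.1% or 8/16 - 5/13 = 11.5%. That fraction of any period effect enters the contrast; it is 0% if losses are balanced. Averaging the sequence-specific paired differences removes it.

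**The case against.** The strongest reply is that this is preference. Protocol 13.1.6 promises descriptive statistics, the SAP delivers them, and the listings let anyone form the pairs. That stands as far as it goes, and it is why this is not an error. But a mean and SD of differences is itself descriptive, and listings leave the reader to compute the contrast for which the design was chosen.

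Four further points stand and limit the claim:
- The precision gain belongs to end-of-period values. Those are exposed to carryover, which has to be said for a product containing a bacterium that Protocol 5.1 describes as a natural colonizer of the intestine.
- The gain may be nil at low rho.
- The bar on formal inference in Protocol 13.1.4 covers safety variables, and hs-CRP is also listed among the safety chemistry tests (Protocol 10.2.6.2, SAP 6.7.3). That section therefore does not clear all six markers equally.
- Protocol 7.2 names no marker for target engagement, and the autism measures go to a plan that is not available.

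The contrast could also sit in the unseen table shells or in the redacted opening of SAP 6.6.2. The redaction leads into the list of autism measures, which lie outside this point. The shells are described as specifying formats. Neither removes the gap in the visible text, but neither can be ruled out.

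A reader might infer that the SAP analyses a crossover as if it were parallel groups, or that its estimates are biased. The documents do not support that: no unpaired interval or test is planned for these markers, and with full completion the observed-value contrast is unchanged.

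**Conclusion.** The point holds as a low-cost improvement. For the six markers, the visible SAP text does not summarise the within-subject SB-121 versus placebo contrast, so the self-control argument of Protocol 7.2 is not reported for them. What is missing is mainly the SD and precision of the difference. At assumed rho 0.3 to 0.7 the half-width would fall from 0.72 SD to between 0.63 and 0.42 SD; at rho 0 it would be slightly wider. These figures rest on full completion, equal SDs and equal correlation, none of which the documents state. The leakage from uneven dropout is illustrative only. Nothing here extends to the autism measures.

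**What to change.** In SAP 6.6.2 add, for each of the six markers, the within-subject SB-121 minus placebo difference in end-of-period values among subjects with both periods: n, mean, SD and a descriptive 95% CI, by sequence and averaged over the two sequences. Label it descriptive with no multiplicity control, and keep every planned summary.

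Three additions belong with it:
- State that a persisting SB-121 shift L in the SB-121-first sequence biases the averaged difference by -L/2.
- Beside it, show the same difference in absolute change from the period-specific baseline as a carryover check, where a usable Period 2 baseline exists. For the stool markers the only between-period sample is at about day 7 of the washout, while SAP 5.1.2 asks for a value after the washout, so the SAP should say what counts.
- For hs-CRP, say that the interval is descriptive and not a formal inferential analysis, or give the mean and SD only.

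The cost is a little table work (one table with six rows could suffice), up to six unadjusted intervals, a headline difference exposed to carryover, and the SAP wording. No extra data or patients are needed.

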6.2. Subject Disposition and Data Sets Analyzed

Subject disposition will be summarized by treatment sequence for the ITT population. The following information will be reported:

- Number and percentage of screened subjects and reasons for screen failure.
- Number and percentage of subjects for the following categories:
 - Randomized,

- Treated in Period 1,
- Not Treated in Period 1,
- Completed Treatment in Period 1,
- Discontinued Treatment in Period 1,
- Reasons for Treatment discontinuation in Period 1,
- Treated in Period 2,
- Not Treated in Period 2,
- Completed Treatment in Period 2,
- Discontinued Treatment in Period 2,
- Reasons for Treatment discontinuation in Period 2,
- Completed the study,
- Discontinued the Study,
- Reasons for study discontinuation.

- Number and percentage of subjects included in each study population

A subject will be regarded as having completed the study if Disposition – End of Study eCRF response to 'Did the subject complete the study?' is Yes. A subject will be considered as having discontinued the study if they have an eCRF response to 'Did the subject complete the study?' of No. Otherwise, the subject will be considered as ongoing in the study.

A listing of all subjects with their treatment and study completion status, including the respective reasons for treatment and study discontinuation will be presented for the ITT population.

A listing of all screen failed subjects with their reasons for screen failure will be presented for all subjects. A separate listing of subjects who failed at least one inclusion / exclusion criteria including a text description of the criterion failed will be presented for all subjects.

A listing of all randomized subjects with their randomization details, including first dose date and actual treatment received will be presented for the ITT population.

A listing of all subjects excluded from at least one analysis population will be presented for the All Screened population.

6.3. Protocol Deviations

All major protocol deviations will be summarized for the ITT population by treatment group as described below:

- The number of unique subjects with at least one major protocol deviation as well as the number of subjects in each major protocol deviation category will be presented by descriptive summary statistics.

A listing of all subjects with one or more protocol deviations will be presented for the ITT population.

6.4. Demographic and Other Baseline Characteristics

6.4.1. Demographic Characteristics

Demographic characteristics will be summarized for the ITT population by treatment sequence and overall as described below. All missing data will be presented as part of a missing category, if appropriate. Standard descriptive statistics will be presented for the continuous variables of:

- Age (years)
- Height (cm) at baseline
- Weight (kg) at baseline
- Body mass index (kg/m²) at baseline

Total counts and percentages of subjects will be presented for the categorical variables of:

- Sex
- Race
- Ethnicity

Demographic characteristics will be listed for the ITT population.

6.4.2. Baseline Characteristics

Baseline characteristics will be summarized for the ITT by treatment sequence and overall as described below. All missing data will be presented as part of a missing category, if appropriate.

Total counts and percentages of subjects will be presented for the categorical variables of:

- ADOS-2 Score at Screening
- DSM-5 checklist at Screening
- Pregnancy test results at Screening
- Drug of abuse at Screening per the urine drug screen

No formal tests of statistical significance will be performed on the demographic and baseline characteristics data.

Baseline characteristics will be listed for the ITT population.

6.4.3. Medical History

Medical history is defined as any condition, with the exception of the study indication, that the subject may have had prior to enrollment in the study, including any chronic conditions diagnosed prior to entry in the study.

Medical history will be coded using the Medical Dictionary for Regulatory Activities (MedDRA) [version 24.0] and will be presented by System Organ Class (SOC) and Preferred Term (PT). Medical history will be sorted alphabetically by SOC and descending frequency of PT.

Medical history records will be summarized for the ITT population by treatment sequence and overall.

Medical history records will be listed by-subject and within-subject by medical history start date for the ITT population.

6.4.4. Prior and Concomitant Medications

All medications will be coded using the WHO Drug Global Dictionary, B3 Sep 2021, Anatomical Therapeutic Chemical (ATC) Classification codes.

Prior medications and concomitant medications are defined as follows:

- Prior medications are those that started prior to the start of dosing in Treatment Period 1.
- Concomitant medications are those with a start date on or after the start of dosing in Treatment Period 1, or those with a start date before the start of dosing in Treatment Period 1 and either a stop date after the start of the Treatment Period 1 or are ongoing during the study.
- If a medication starts prior to dosing in Treatment Period 1 and continues after dosing in Treatment Period 1 has started, it will be considered both prior and concomitant.

See Section 5.2.3 for imputation of missing or partial dates for medication.

Prior medications will be summarized for the ITT population by treatment sequence and overall, and concomitant medications will be summarized separately for the ITT population by treatment group as follows:

- The number and percentage of subjects with at least one prior/concomitant medication will be presented.
- The number and percentage of subjects with at least one prior/concomitant medication within each Anatomical Group (ATC Level 1) and preferred term will be presented. The summary will be sorted using numerical counts by descending order of Anatomical Group, then descending order of preferred term in the total column. Where groups or terms tie these will be sorted alphabetically.

Prior medications and concomitant medications will be listed separately for the ITT population. In the listings, the relative start and stop day of prior medication use will be calculated relative to the first dose date of Treatment Period 1. In the listings, the relative start and stop day of concomitant medication use will be calculated relative to the first dose date of treatment in the period when the medication started and will be presented for those subjects who received at least one dose of treatment. Only original dates will be presented in the listing even though the relative day may be based on an imputed date.

6.5. Measurements of Treatment Compliance

Treatment compliance is defined as the number of doses that were actually taken relative to the number of doses that should have been taken as per the protocol for the duration of actual treatment exposure.

In general, the percentage overall compliance, assessed by dose count for each Treatment Period, will be calculated as follows:

$$\text{Compliance (\%)} = \frac{(\text{Number of kits dispensed} - \text{Number of kits returned})}{\text{Number of days on treatment} \times \text{Number of kits prescribed per day}} \times 100\%$$

Number of days on treatment will be calculated as follows:

$$(\text{last dose date of treatment in a Treatment Period} - \text{first dose date of treatment in a Treatment Period}) + 1$$

The calculated percentage compliance will be categorized as:

- < 80% compliance
- $\geq 80\%$ compliance

Compliance will be summarized for the ITT population by treatment group as follows:

- Percent compliance will be presented by summary statistics.
- Number and percentage of subjects within each of the compliance categories will be presented. Any subjects with missing data will be presented as part of a “Missing” category.

Treatment compliance will be listed together with exposure for the ITT population. Missing data will not be imputed and only original data for those fields (for example, date fields) will be presented in the listing together with derived variables such as the calculated compliance (%) and exposure duration.

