10.2.3 Treatment Visit – Day 1 (See Schedule of Events Section 2.2)

Following confirmation of eligibility criteria, subjects will be randomized to receive SB-121 or placebo. Subjects will undergo study-specific procedures on Day 1 in accordance with the Schedule of Events.

Following baseline tests, all subjects will be given their first dose of either SB-121 or placebo at the clinic. The IP will be prepared according to the provided Daily Medication Instructions.

All subjects receive an additional 27 doses of IP to be self-administered once daily at home at about the same time every day (e.g. around breakfast). In addition to the 27 oral doses, additional material will be provided for use in the event of spillage. Refer to the Daily Medication Instructions

for details on IP storage, reconstitution and consumption. All subjects will be instructed to capture the date and time of each dose of IP on the Patient Diary.

Subjects will be discharged after all Day 1 evaluations have been completed.

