13.1.3 Exposure and Compliance

Medication compliance will be monitored via Patient Diary as well as during follow-up calls and at the end of each study treatment phase, as noted in Schedule of Events (Section 2.2). Subjects will be asked to return all their medication vial(s), including all empty vials, at the end of each treatment period. Study drug compliance will be assessed by the study staff by recording bottle counts of study treatments.

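### SAP 6.5 defines compliance as doses taken but computes kits dispensed minus kits returned, so returned empties lower the figure and spilled, lost or kept kits raise it

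*SAP*

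**What the plan says.** **Definition and formula.** SAP 6.5 opens: "Treatment compliance is defined as the number of doses that were actually taken relative to the number of doses that should have been taken". It describes the percentage as "assessed by dose count for each Treatment Period". The numerator is then kits dispensed minus "Number of kits returned". The denominator is days on treatment times kits prescribed per day, where days run from the first dose date to the "last dose date of treatment in a Treatment Period", both inclusive. Results are split at 80%, the lower category being "< 80% compliance", and are summarised by treatment group.

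**Returns.** Protocol 13.1.3 states: "Subjects will be asked to return all their medication vial(s), including all empty vials, at the end of each treatment period". Site staff then record bottle counts. The diary and the follow-up calls are named there as further monitoring.

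**Spares and dose records.** Protocol 10.2.3 provides for 27 home doses after the clinic dose and adds that "additional material will be provided for use in the event of spillage". No quantity is given. The same section says: "All subjects will be instructed to capture the date and time of each dose of IP on the Patient Diary". SAP 6.5 does not use that record.

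**The concern.** Dispensed minus returned equals doses taken only under two conditions: returned kits must mean kits returned unused, and every kit not taken must come back. SAP 6.5 states neither. The protocol's return instruction pulls against the first, because empties come back too. The spillage supply pulls against the second, because a spilled kit is neither taken nor returned unused.

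After Day 1 of period 1, dosing takes place largely at home. Compliance by treatment group is one of the items a reader will use to judge whether a quiet safety profile or an unchanged biomarker reflects real intake of SB-121. With the planned maximum of 16 subjects, each contributing to both treatments, one subject placed on the wrong side of 80% moves that category by 1/16 = 6.25 percentage points.

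**Working it through.** The documents give no compliance result to reproduce, so the formula is evaluated directly.

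**Inputs**
- Formula (SAP 6.5): 100 × (dispensed − returned) / (days × kits per day).
- Days = 28, the nominal treatment period.
- One kit per dose and one dose per day. The first part is an assumption: the SAP counts kits, Protocol 13.1.3 counts bottles, and Protocol 7.1 says two bottles are combined. The packaging text that might link these units is not available.
- Kits neither taken nor returned: 1 to 3, an assumption. The upper end comes from the gap between 30 home doses (Protocol Synopsis, Study Design) and 27 (Protocol 10.2.3). With the clinic dose this gives up to 31 kits dispensed.
- Cut: 0.80 × 28 = 22.4, so 23 doses are needed to reach 80%.

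**Check case.** 31 dispensed, 28 taken, 3 returned unused: (31 − 3)/28 = 100%. The formula works when both conditions hold.

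**Reading 1: any returned kit counts, empties included** (fully adherent subject, 31 dispensed, 3 unused returned)
- 5 empties counted: (31 − 8)/28 = 82.1%.
- 6 empties counted: (31 − 9)/28 = 78.6%, below the cut.
- All 28 empties counted: (31 − 31)/28 = 0%.

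**Reading 2: only unused kits count as returned.** Dispensed − returned is then doses taken plus missing kits (spilled, lost or kept), so the score is (taken + missing)/28.

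| Doses taken | Doses taken / 28 | 1 missing | 2 missing | 3 missing |
|---|---|---|---|---|
| 28 | 100.0% | 103.6% | 107.1% | 110.7% |
| 22 | 78.6% | 82.1% | 85.7% | 89.3% |
| 21 | 75.0% | 78.6% | 82.1% | 85.7% |
| 20 | 71.4% | 75.0% | 78.6% | 82.1% |

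One missing kit is enough to carry a subject with 22 doses over the cut.

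**Clinic dose.** SAP 6.5 does not say whether the supervised first dose is a dispensed kit. If it is not, a subject with 23 doses (23/28 = 82.1%) shows 22/28 = 78.6%, an error in the other direction.

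**Check of the remedy** (31 dispensed, spares and clinic dose included; kit count = dispensed − returned unused − documented spilled or lost)
- 28 taken, 3 returned unused: 31 − 3 − 0 = 28, or 100%.
- 28 taken, 3 spilled: 31 − 0 − 3 = 28, or 100%.
- 22 taken, 6 returned unused, 3 documented lost: 31 − 6 − 3 = 22, or 78.6%.
- 22 taken, 6 returned unused, 3 kept without record: the kit count is 31 − 6 = 25 against 22 in the diary. The difference of 3 shows up and can be queried.

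**The case against.** **The 0% result.** A reader might infer that every subject who follows the return instruction will be reported at 0%. The documents do not support that. SAP 6.5 opens with doses taken, refers to a dose count and offers the formula only as the general case. Most programmers would read returned as unused. The SAP also counts kits where the protocol counts vials and bottles, so whether an empty vial could be a returned kit is not known. The 0% figure is the extreme of a literal reading, not an expected result. What stands is that the SAP leaves the reading open while the protocol brings empties back.

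**Spares.** The range of 1 to 3 is assumed, and the high scores need kits to be spilled, lost or, against instruction, kept. If every untaken kit comes back unused, the formula is right. That is fair, but spillage is foreseen by the protocol itself and needs no breach by the subject. Protocol 9.9 requires spilled and lost product to be documented, so the information to correct for it should exist. The formula does not use it.

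**Consequence.** A reader might also infer that under-exposure would be concealed or that results would be compromised. That goes too far. SAP 6.7.1 derives exposure separately per period, less off-treatment days, and lists it with compliance. The SAP's populations are All Screened, ITT and Safety; none uses the 80% cut, and no test depends on it.

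**Diary or count.** Protocol 13.1.3 names bottle counts as the assessment, so a count-based formula follows the protocol, and putting the diary first is a judgement. A count kept as the primary measure would still need the same corrections.

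**Conclusion.** The point holds as a mismatch between definition and formula. Under either reading of returned, SAP 6.5 can report something other than doses taken: too low if empties are counted, too high for each spilled, lost or kept kit. On the stated assumptions (28 days, one kit per dose, 1 to 3 missing kits), the overstatement is 3.6 to 10.7 percentage points. That is enough to show values above 100% and to move a subject with 20, 21 or 22 doses across 80%, given 3, 2 or 1 missing kits respectively. The TFL shells may contain a further rule; none appears in the protocol or SAP. The impact is limited to a descriptive table, but the reported number would change and the correction is inexpensive, so it should be made.

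**What to change.** Rewrite the SAP 6.5 calculation as follows.

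1. Per period, compliance = doses recorded as taken in the diary, plus the supervised clinic dose (counted once), divided by doses due over the days on treatment.
2. Reconcile it with a kit count: all kits dispensed, spares and clinic dose included, minus kits returned unused, minus kits documented as spilled or lost. List the discrepancies.
3. Keep spares on both sides of that count. If they are left out of dispensed but counted when returned, a fully adherent subject who hands back 3 unused spares scores (28 − 3)/28 = 89.3%.
4. State how bottles map to kits and to doses.

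Separately, the sponsor must reconcile the dose numbers. The Protocol Synopsis under Study Design gives 30 home doses after the clinic dose in period 1 and 30 doses in period 2, while its Treatment Regimens entry and Protocol 10.2.3 give 27 home doses. These figures determine what is dispensed and what counts as due.

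The cost is SAP wording and programming on diary and accountability data that the protocol already requires. The small downside is reliance on self- or caregiver-report, which the kit count checks.
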